7 STATISTICAL METHODS

7.1 General statistical conventions

All statistical procedures will be completed using SAS GRID Linux/SAS Studio version 9.4.

Unless otherwise stated, all statistical testing will be two-sided and will be performed using a significance (alpha) level of 0.05. Two-sided 95% confidence intervals (CI) will be provided when relevant.

Continuous variables will be summarized using descriptive statistics, including number of subjects (n), mean, geometric mean (for efficacy endpoints only), first quartile (Q1), median, third quartile (Q3), standard deviation (SD), minimum and maximum.

Categorical variables will be summarized using frequency counts and percentages in each category. The denominator for all percentages will be the number of subjects in that treatment group within the population of interest, unless otherwise noted. Percentages will be rounded to one decimal place.

For summary purposes, baseline will be defined as the last available OLE pre-dose value; all summaries will be presented by treatment group assigned in the double blind study (XPF-009-301) and overall, unless otherwise specified.

➢ XEN496 Only

(Subjects who received XEN496 in the primary study and continue to receive XEN496 at the same dose throughout the OLE)

Placebo to XEN496

(Subjects allocated to placebo in the primary study and received XEN496 in OLE)

> Total

All subject data, will be presented in individual subject data listings. Unless otherwise stated, unscheduled visit results will be included in date/time chronological order, within subject listings only. The treatment group as well as subject's sex and age will be stated on each listing. Unless otherwise stated, data listings will be based on all enrolled set.

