5.4 Secondary Efficacy Analysis Set

The secondary efficacy analysis set includes those subjects who were treated in both the preceding primary study (XPF-009-301) and the current OLE study, with at least 1 evaluable seizure data in both study periods.

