6.1.1 Efficacy Variables

6.1.1.1 Seizure frequency

Caregivers will record all countable motor seizures in the daily seizure diary, which will be reviewed at selected visits as specified in Table 2 and Table 3. The following motor seizures with a duration of at least 3 seconds will be recorded in the seizure diary:

[figure not shown]
- Focal tonic.
- Focal motor.
- Focal with secondary generalization.
- Generalized tonic.
- Focal clonic.
- Generalized clonic.
- Generalized tonic-clonic.

[figure not shown]
Important exclusions to the countable seizures are:

- Single myoclonic jerks.
- Staring spells without a motor component.

If epileptic spasms are suspected or reported, the investigator must be contacted immediately to confirm the diagnosis and to initiate treatment.

The denominator will be based on those evaluable days when an entry of yes or no is provided on occurrence of seizure of any type. Days with counts of 0 seizure will be included in the denominator; while days with missing seizure counts will be excluded from the denominator.

The average monthly seizure frequency (per 28 days) will be derived with the formula below:

sum of daily countable seizure counts reported during the placebo (or XEN496) treatment period

Total number of days within the time period when seizure data is reported $\times 28$

Percent change of average monthly seizure frequency will be derived using the below formula where *average monthly seizure frequency* is defined as above and *Baseline* refers to the comparator period appropriate for the endpoint (eg. placebo period for the key efficacy endpoint and the pre-randomization baseline period for other efficacy endpoints):

Average monthly seizure frequency – Baseline average monthly seizure frequency Baseline average monthly seizure frequency × 100

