7.2 Subject disposition

Subject disposition information will be summarized by treatment group in OLE period and overall. The disposition summary will include the number and percentage of subjects meeting the following criteria:

- Screened
- Screen failed
- Received a dose in OLE period
- Completed treatment
- Discontinued treatment

Statistical Analysis Plan Protocol Number: XPF-009-302

- Reasons for discontinued treatment
- Completed the study
- Completed the Taper period
- Completed Follow Up
- Discontinued from the study
- Reasons for discontinuation from study

The number of subjects who took a dose in OLE period will be used as the denominator for the percentage calculation. Subject disposition will be listed for subjects who signed informed consent form. Details of eligibility criteria for enrollment will be listed separately.

The number and percentage of subjects in each analysis set and reason for exclusion will also be tabulated separately. Population membership details will be listed, including reason for exclusion from each population

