7.6.2 Analysis of additional efficacy endpoints

Analyses of additional secondary efficacy endpoints will primarily be descriptive based on the secondary efficacy analysis set.

For the summary of data from the OLE only, a combined treatment group including those subjects treated in OLE will be included. For the summary of endpoints with a combined database from both the primary study (XPF-009-301) and the OLE study, the data will be presented by treatment group in the primary study (XPF-009-301). Data after switching from placebo to XEN496 will be clearly identified.

7.6.2.1 To assess the long-term effect of XEN496 on seizure reduction in pediatric subjects treated with XEN496

- Change from pre-randomization baseline (double blind baseline, refer Section 7.1) in the previous study over time based on response categories (<25%, 25 to <50%, 50 to <75%, 75 to <100%, 100%), based on estimated seizure frequency every 3 months during the OLE period. Proportion of subjects achieving a reduction in 3 months (90 day) seizure frequency from baseline of <25%, 25% to <50%, 50% to <75%, 75% to <100%, and 100% will be summarized using count and percentage. (refer section 6.1.1 for details).
- Descriptive summary will be given for percent change from baseline in countable motor seizure frequency, relative to pre-randomization baseline of the previous study (XPF-009-301), assessed over time every 3 months during the OLE.
- Descriptive summary will be provided for percent change from baseline in countable motor seizure frequency, relative to pre-randomization baseline of the previous study (XPF-009-301), for every 3 months based on combined data from both XPF-009-301

and the OLE, by the treatment group in the previous study.

7.6.2.2 To evaluate Caregiver Global Impression of Severity (CaGI-S) and Caregiver Global Impression of Change (CaGI-C) scores

The CaGI-S for overall condition and seizure severity will be summarized at baseline (OLE Baseline and double-blind baseline) and each of the post-baseline visit using number and percent. Change from baseline (OLE Baseline and double-blind baseline) to post baseline will also be summarized.

The CaGI-C will be summarized at each of the post-baseline visit using counts and percentage for the following domains: overall condition, seizures, behavior, alertness, motor skills, visual function, and communication.

Listings will be provided for CaGI-S and CaGI-C scores.

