7.6.2.4 To evaluate the investigator's global impression change (CGI-C)

Change over time in subject's seizures and overall condition will be assessed using an investigator-assessed CGI-C scale. Response to CGI-C scale category will be summarized at each of the scheduled visits. Individual listing will be provided for CGI-C score.

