7.7.5 Electrocardiograms

Observed and changes from OLE baseline of continuous ECG measurements will be summarized by treatment group and age groups (1 to 12 months and >12 to 84 months) at each scheduled visit. Additional summaries will be provided for ECG interpretation and will be summarized using frequency tables. Shift from baseline to post-baseline will also be provided for the ECG interpretation.

Potentially clinically significant abnormality categories listed below will be summarized using count and percentage.

Variable Name	Age group	Criterion
	NA	<= 300
QT interval corrected for heart rate by		>= 60 msec increase from
Fridericia's formula (QTcF) (msec)		baseline
		>= 500
OT Interval (msec)	NA	<= 300
QT Interval (msec)		>= 600
	1 to 12 months	>= 86 or $>=25%$ increase
OBS Interval (maga)		from baseline
QRS Interval (msec)	>12 to 84	>= 95 or $>= 25%$ increase
	months	from baseline
DP Internal (maga)	1 to 12 months	>= 141 or >= 25%
PR Interval (msec)		increase from baseline
	>12 to 84	>= 155 or $>= 25%$ increase
	months	from baseline
Haart rate (hpm)	1 to 12 months	>= 194
Heart rate (bpm)		<= 106
Haart rate (hpm)	>12 to 84	>= 123
Heart rate (bpm)	months	<= 62

Table 6: Potentially Clinically Significant ECG Abnormality Criteria

Listings will be provided for ECG data and potentially clinically significant abnormalities will be flagged in the listing.

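### SAP 7.1 divides by-visit and 3-month-window percentages by the full treatment group, so unassessed children count as not abnormal and fall in no response or rating category

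*SAP*

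**What the plan says.** The general rule is in SAP 7.1: "The denominator for all percentages will be the number of subjects in that treatment group within the population of interest, unless otherwise noted". The analysis sets in section 5 are fixed lists of children and do not change from visit to visit.

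The one other denominator of subjects in the visible text belongs to the disposition table in 7.2: "The number of subjects who took a dose in OLE period will be used as the denominator for the percentage calculation". That denominator is also fixed.

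Several tables are explicitly repeated over time:

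- **Response categories (7.6.2.1).** Every 3 months in the OLE the SAP tabulates the "Proportion of subjects achieving a reduction in 3 months (90 day) seizure frequency from baseline", in five bands. These "will be summarized using count and percentage. (refer section 6.1.1 for details").
- **CaGI-S and CaGI-C (7.6.2.2).** Numbers and percentages are given at each post-baseline visit.
- **CGI-C (7.6.2.4).** "Response to CGI-C scale category will be summarized at each of the scheduled visits". Under 7.1, categorical variables receive counts and percentages.
- **Laboratory shifts and PCSA (7.7.2).** Shifts are tabulated at each visit, and PCSA incidence at each scheduled visit.

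The efficacy tables use the secondary efficacy set (5.4), which a child enters "with at least 1 evaluable seizure data in both study periods".

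**The concern.** Treatment lasts 36 months. The SAP foresees early dropout (6.2.1) and visits affected by COVID-19 (7.3), so some children will have no assessment at some visits. Under the 7.1 rule they stay in the denominator and can never appear in the numerator.

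For laboratory abnormalities this amounts to treating an unassessed child as a child without the abnormality. Long-term safety is the primary objective, and the error runs in the drug's favour.

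For the response and rating tables the missing children are in no category. The rows stop adding to 100%, and a trend over time mixes the effect on the children with the loss of assessments. If the groups from the primary study lose children at different rates, the tables can show a difference between them that comes from attrition alone.

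**Working it through.** **Is there an override?**

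1. Section 7.2 concerns disposition only, and its denominator is fixed.
2. The response-category text points to 6.1.1. The denominator there is diary days within a child: "days with missing seizure counts will be excluded from the denominator". It does not say which children are counted.
3. Section 6.2.1 describes multiple imputation for the key efficacy endpoint only. It says nothing on by-visit or by-window percentages.
4. Entry to the secondary efficacy set needs a single evaluable seizure datum in each study. A child with early OLE data and nothing later therefore remains in the set for every later window.
5. No missing row and no non-responder rule is stated for any of these tables.

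So the 7.1 default governs them.

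**What the default does.** Let N be the number in the group, m the number assessed at the visit, and x the number in a category.

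Printed % = x/N = (x/m) × (m/N) = rate among assessed × fraction assessed.

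The five response categories together contain m children, so they sum to m/N.

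**Inputs.** N = 40 is the approximate total in SAP section 4. The fraction not assessed, the 10% abnormality rate and the 50% response rate are assumptions. The documents give none of them, so there is no figure in the plan to reproduce.

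| Not assessed | m of 40 | Five categories sum to | 10% abnormality prints as (expected) | 50% response prints as |
|---|---|---|---|---|
| 0% | 40 | 100% | 10% | 50% |
| 10% | 36 | 90% | 9% | 45% |
| 20% | 32 | 80% | 8% | 40% |
| 30% | 28 | 70% | 7% | 35% |
| 40% | 24 | 60% | 6% | 30% |
| 50% | 20 | 50% | 5% | 25% |

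For the 30% row: 28/40 = 70%; 10% × 0.70 = 7%; 14/40 = 35%, against 14/28 = 50% among those assessed. In whole children, 3 abnormal results among 28 assessed print as 3/40 = 7.5% rather than 3/28 = 10.7%.

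For the response table to stay flat at 50% with 30% not assessed, response among assessed children would have to rise to 0.50/0.70 = 71.4%.

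**By prior arm.** Assume 20 children per arm, 50% response in both, and 10% against 30% not assessed. Responders are 9 of 18 and 7 of 14. The table prints 9/20 = 45% and 7/20 = 35%, a 10-point gap with no difference in response.

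**Is the fixed N a non-responder analysis?** Not as written. The SAP does not declare one, and the lowest category (under 25% reduction) shrinks with attrition like the others. The missing children are not placed among the non-responders.

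**Does an assessed-children denominator settle the response table?** Not alone. Suppose 24 of 40 children respond and the 16 non-responders then leave. The full-set figure stays at 24/40 = 60%, while the observed-case figure becomes 24/24 = 100%. Each denominator can mislead, so the response table needs both.

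**The case against.** The strongest defence is that 7.1 is only a default. It gives way where otherwise noted, and the table templates are in a separate document that may specify by-visit denominators. That is possible. But the SAP is the governing text, and as it stands a programmer who follows it obtains the results above.

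The second defence is that little depends on these tables. Section 7.6.2 calls the additional efficacy analyses primarily descriptive. The one specified test, the Wilcoxon signed-rank test on the key endpoint, uses no percentage. Counts are shown beside percentages, and laboratory abnormalities are flagged in listings, so with about 40 children no abnormal case is hidden. This stands, and it limits the severity.

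The third is that, for response, a full-set denominator is the cautious choice if non-responders tend to leave. This also stands, and it is why observed-case rates should not simply replace the full-set version.

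A reader might extend the point to ECG and vital-sign abnormalities. The documents do not support that. The ECG sentence reads "Potentially clinically significant abnormality categories listed below will be summarized using count and percentage" and does not say by visit, and the vital-sign text is no clearer. In both sections the per-visit wording belongs to the observed values and changes from baseline. A table of any post-baseline occurrence over the full safety set is an ordinary reading, and percentages in it need not fall visit by visit.

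A reader might also infer that the infant rows of the ECG table are divided by all children. The SAP does not say so. The criteria table has an age-group column, and using the band as the denominator is at least as natural. The denominator there is unstated rather than shown to be wrong.

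**Conclusion.** The point holds for the tables that the SAP explicitly repeats by visit or 3-month window: response categories, CaGI-S, CaGI-C, CGI-C, laboratory shifts and laboratory PCSA. For these the stated default understates by-visit laboratory abnormality rates and leaves response and rating categories summing to less than 100%.

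The identity is exact, but its size depends on attrition, which the documents do not give. At an assumed 30% not assessed, every such percentage is 0.70 of the rate among assessed children. A rising true rate could mask the fall, and informative dropout could make the full-set response figure the less misleading of the two.

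A reader might conclude that every percentage in the report is wrong, or that adverse event rates are affected. Neither follows. The default can be overridden, and the safety set definition and the adverse event text are not visible, so nothing is counted against the plan there.

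Severity: minor to moderate.

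**What to change.** Amend SAP 7.1, and carry the rule into the table templates:

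- **Laboratory shifts, laboratory PCSA, CaGI-S, CaGI-C and CGI-C by visit.** The denominator is the children in the group with a non-missing assessment at that visit. A baseline value is also required for shift tables and change criteria. Print n/m (%).
- **3-month response categories.** Show the number evaluable in each window and the observed-case percentage. Beside it, show a full-set version, labelled as such, with either an explicit missing row or a declared non-responder rule.
- **Age-specific ECG criteria.** State that the denominator is the children in that age band with an ECG.

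The cost is a short SAP amendment, slightly more programming and one extra response display. No new data are needed.

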7.2 Subject disposition

Subject disposition information will be summarized by treatment group in OLE period and overall. The disposition summary will include the number and percentage of subjects meeting the following criteria:

- Screened
- Screen failed
- Received a dose in OLE period
- Completed treatment
- Discontinued treatment

Statistical Analysis Plan Protocol Number: XPF-009-302

- Reasons for discontinued treatment
- Completed the study
- Completed the Taper period
- Completed Follow Up
- Discontinued from the study
- Reasons for discontinuation from study

The number of subjects who took a dose in OLE period will be used as the denominator for the percentage calculation. Subject disposition will be listed for subjects who signed informed consent form. Details of eligibility criteria for enrollment will be listed separately.

The number and percentage of subjects in each analysis set and reason for exclusion will also be tabulated separately. Population membership details will be listed, including reason for exclusion from each population

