3 STUDY DESIGN

3.1 General study design

This is a Phase 3, open-label, long-term extension study to evaluate the safety, tolerability, and efficacy of XEN496 administered as adjunctive therapy in pediatric subjects with KCNQ2-DEE who participated in the primary study, XPF-009-301.

Approximately 40 subjects may be included in the study based on the anticipated number of subjects who could roll over from Study XPF-009-301.

Subjects will undergo the following:

- Screening/Baseline period Subjects will undergo eligibility assessment at Visit 22 or early termination in the primary study (XPF-009-301).
- Treatment period 36 months:
 - Blinded transition/titration period
 - Open-label period approximately 35 months.

Subjects who received XEN496 in the primary study will continue to receive XEN496 at the same dose throughout the OLE.

[figure not shown]
Subjects allocated to placebo in the primary study will be required to begin a titration of XEN496 CCI

- CCI
- Taper period CCI
 Subjects who discontinue or complete the study treatment will be required to taper off study drug CCI
 The actual duration of the taper period will depend on the subject's dosage prior to taper.
 - Follow-up Approximately 4 weeks after subjects have tapered off of study drug.

Total study duration per subject is estimated to be 37 months.

The Study Design Schematic is presented in Figure 1.

Figure 1: Study Design Schematic

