4 SAMPLE SIZE DETERMINATION

No formal sample size calculation has been performed. Only those subjects who have completed the previous study, XPF-009-301, are eligible to be enrolled into this study. Therefore, the expected total sample size will be up to approximately 40 subjects.

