5 ANALYSIS POPULATIONS

5.1 Enrolled Set

Enrolled set include all subjects who signed the informed consent form.

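### SAP 7.2 divides the Screened and Screen failed counts by the number dosed in the extension, so one screen failure puts Screened above 100% and overstates the failure rate

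*SAP*

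**What the plan says.** SAP section 7.2 (Subject disposition) opens with "The disposition summary will include the number and percentage of subjects meeting the following criteria". The list starts with Screened, then "Screen failed", then "Received a dose in OLE period". It continues with completion and discontinuation of treatment and of the study, the taper period and follow-up.

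After the list, one rule covers the percentages: "The number of subjects who took a dose in OLE period will be used as the denominator for the percentage calculation". No row is exempted.

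Two other places bear on this:

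- SAP section 7.1 gives a general convention: "The denominator for all percentages will be the number of subjects in that treatment group within the population of interest, unless otherwise noted". Section 7.2 does note otherwise, so its own rule takes precedence.
- SAP section 5.1 defines a wider set: "Enrolled set include all subjects who signed the informed consent form". Section 7.2 uses signed consent to decide who appears in the disposition listing, but not as a denominator.

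**The concern.** A percentage in a disposition table should be a share of a group that contains the subjects being counted. Subjects dosed in the extension are such a group for the completion, discontinuation, taper and follow-up rows. They are not for the screening rows, because a child who fails screening is not dosed. Three consequences follow from the rule as written:

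- Screened is divided by a smaller group than itself whenever anyone fails.
- Screen failed becomes a ratio of failed to dosed and not a rate.
- Received a dose is divided by itself and carries no information.

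Screen failures are possible here. Eligibility is assessed at the last visit or at early termination of the primary study (SAP 3.1). The protocol synopsis asks for completion of the primary study (or withdrawal for protocol-specified worsening), at least 85% diary compliance, and no adverse event judged to preclude entry. At stake is the planned percentage summary of loss at the entry step, in a study whose primary objective is long-term safety.

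**Working it through.** **The plan's own figure.** There is none to reproduce. The documents give no disposition counts, and section 4 states that no formal sample size calculation was done.

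**Inputs**

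- S = number screened, set to 40. This is an assumption, scaled to SAP section 4: "Therefore, the expected total sample size will be up to approximately 40 subjects". SAP 3.1 ties a similar figure to the anticipated number who could roll over.
- F = number who fail screening. The documents give no value, so it is varied over 0, 1, 2, 4 and 8.
- D = number dosed in the extension = S − F. This assumes that everyone screened but not dosed is a screen failure.

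**Formulas**

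- Section 7.2 as written: Screened % = 100 × S/D; Screen failed % = 100 × F/D; Received a dose % = 100 × D/D = 100.
- Screened as denominator: Screened % = 100 × S/S = 100; Screen failed % = 100 × F/S; Received a dose % = 100 × D/S.
- Overstatement of the failure rate: (F/D) ÷ (F/S) = S/D, which exceeds 1 whenever F ≥ 1.

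**Results with S = 40**

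| F | D | Screened, as written | Screen failed, as written | Screen failed, true | Received a dose, as written | Received a dose, true |
|---|---|---|---|---|---|---|
| 0 | 40 | 100.0% | 0.0% | 0.0% | 100.0% | 100.0% |
| 1 | 39 | 102.6% | 2.6% | 2.5% | 100.0% | 97.5% |
| 2 | 38 | 105.3% | 5.3% | 5.0% | 100.0% | 95.0% |
| 4 | 36 | 111.1% | 11.1% | 10.0% | 100.0% | 90.0% |
| 8 | 32 | 125.0% | 25.0% | 20.0% | 100.0% | 80.0% |

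For example, with F = 4: 40/36 = 111.1%, 4/36 = 11.1%, 4/40 = 10.0%, 36/40 = 90.0%.

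**If 40 is read as the number dosed.** Then 1, 4 or 8 failures mean 41, 44 or 48 screened. Screened prints as 102.5, 110.0 or 120.0%. Screen failed prints as 2.5, 10.0 or 20.0%, against 2.4, 9.1 or 16.7%. The pattern is the same, but this reading needs more screened subjects than the roughly 40 expected to roll over, so the table above is the better guide to size.

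**The case against.** The strongest case on the other side is that nothing is lost. Section 7.2 asks for counts beside the percentages. It also plans a disposition listing for all who signed consent, a separate listing of eligibility details, and a table of analysis sets with reasons for exclusion. A reader can take the printed counts and compute the rate. With no failures, or one or two among 40, the distortion in the failure rate is nil or a few tenths of a point. The table shells are a separate document (SAP section 1) and may already show counts only on the screening rows. All of this stands, and it keeps the point at the lowest severity. It does not make the written rule correct. Section 1 also requires departures from the SAP to be described and justified in the study report, so a programmer who used a sensible denominator would create a deviation.

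A reader might infer two stronger things that the documents do not support:

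- **That the failure percentage is the only measure of how selected the long-term safety group is, and that it is lost.** The counts and listings above contradict this. The percentage is also a limited measure under either denominator. Several entry criteria are settled by primary-study data, so children who fail them may never sign consent for the extension and would appear in neither figure.
- **That the rule exaggerates a difference in screening loss between the primary-study arms.** This depends on how the columns are built, which is unsettled. Section 7.2 summarises by treatment group in the extension. Section 7.1 refers to the double-blind assignment but describes the two groups by what subjects received in the extension. A screen failure received nothing there and might appear only in the total column. The documents also give no counts by arm.

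**Conclusion.** The rule in SAP 7.2 is wrong as written for the first three disposition rows. The fault is structural: the Screen failed numerator is never contained in its denominator, and Received a dose is 100% by construction. The visible error needs at least one screen failure. Assuming 40 screened and 1 to 8 failures, Screened prints between 102.6% and 125.0%, and the failure rate is overstated by a factor of about 1.03 (40/39) to 1.25 (40/32). With no failures the printed figures are correct.

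The failure counts, and the use of 40 as the number screened, are assumptions. The conclusion concerns the SAP text alone, because the shells could not be checked. It is a presentation error in one descriptive table. No endpoint, test, analysis set, or efficacy or safety result changes.

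**What to change.** In SAP 7.2, replace the single denominator sentence with two rules:

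1. For Screened, Screen failed and Received a dose, the denominator is the number screened, meaning all who signed consent (the Enrolled Set of section 5.1). Show these rows overall. If they are also shown by group, use the arm assigned in the primary study, because a screen failure has no treatment in the extension.
2. For the treatment, study, taper, follow-up and discontinuation rows, the denominator stays the number dosed in the extension.

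The visible text does not define Screened, and section 5.1 does not say which consent form it means. The revised sentence should state that both refer to consent for the extension study, if that is the intent.

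The cost is a change to one sentence in the SAP and one denominator in the disposition program, plus a check that the table shell agrees. No new data are needed.
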